## 11. Methods

Study design: A randomized, multicentric, open-label, controlled trial

Study population: Critically ill patients on mechanical ventilation with AKI and CRRT requirements admitted with COVID-19 disease in any of the two participant institutions.

Participating institutions: INCMNSZ , INER

Timing: October 02th, 2020 to December 30th, 2021.

Interventions: patients meeting inclusion criteria and accepting to participate in this study with informed consent (or legal representative via phone call giving the pandemic lockdown), will be randomized to be treated with CRRT using the AN-69 Oxiris membrane or standard AN-69

membrane (Figure 1). Randomization will be performed on the day of admission using online software (EPIDAT 4.2). The intervention will be sustained during 72 continuous hours.

Patients will be randomized to use one of the following membranes (Figure 1):

CRRT using the AN69 Oxiris membrane (intervention group)

CRRT using the standard AN69 membrane (control group)

\*\*\*Given the pandemic lockdown, informed consents for hemodialysis treatment have been collected by phone call. The study protocol and therapeutic options will be presented to the next of kin; in case of approval for study entry, the date and hour will be registered and a formal appointment for signing the informed consent will be scheduled.

#### Monitoring of interventions

- Blood samples will be drawn, every 8 hours during the 72 hours of treatment, to measure cytokine serum levels (IL-6,IL-10,TNF alfa).
- All renal replacement therapy prescriptions (control and intervention group) will be standardized as follows:
  - o Vascular access: 12 French,double-lumen, a high-flux catheter placed into the internal jugular vein or femoral vein (either right or left-sided)
  - o The dose of CRRT will be set at 30ml/kg/h, using ideal body weight.
  - o CRRT modality: Continuous veno-venous hemodiafiltration
  - o Anticoagulation: Regional citrate anticoagulation will be used (Gambro Prismocitrate 18/2-citrate 18 mmol/L). The goal level of ionized calcium in the circuit will be 0.2-0.4 mmol/L. Initial citrate dose will be determined according to the processed blood volume, maintaining a blood flow of 150mL/min, in close relation to a citrate dose of 2.5-5mmolL. Calculations to determine initial citrate dose will be performed using Adequator mobile application, which is widely available and validated for its use. An intravenous calcium infusion will be used to counteract the citrate effect, via a 17.4% calcium gluconate solution to sustain ionized serum calcium between 1.1-1.29 mmol/L in the arterial line.
  - o The Post-dilution substitution fluid rate will be set at 150mL/h.
  - o The dialysate flow rate will be determined as the remaining fluid obtained using the following formula:  
§  $\text{Dialysate} = \text{Total effluent dose} - (\text{citrate infusion rate} + \text{post-dilution substitution fluid rate} + \text{ultrafiltration rate})$
  - o The ultrafiltration rate will initiate at 100mL/hour the first 4 hours and adjusted in according to the patient clinical status and attending physician judgment.
  - o PrismaB/22 (K+ 4, zero-calcium) will be used as a substitution and dialysate fluid.
- Citrate-based anticoagulation monitoring and dosing will be performed using blood gas analysis of samples drawn from both the circuit and patients, according to institutional protocols previously used (described in supplemental material 1).
- Serum electrolytes will be tracked and adjusted using the institutional protocol, which is described in detail in the supplemental material.
- CRRT membrane will be replaced every 24 hours, regardless of the group.
- CRRT treatments will be performed using Prismaflex or PrismaX machines.

- Effluent delivered dose will be examined using pre-filter BUN and post-filter BUN, according to KDIGO guidelines for acute kidney injury.

Interventions and treatments unrelated to renal support therapies.

- Every patient enrolled in the trial will receive the standard of care according to the attending physician criteria and institutional protocol established in the participant centers.
- In case the patient is receiving antibiotics, the doses administered will remain unadjusted during the 72h period of the study.
- Norepinephrine will be the first-line vasopressor used to maintain MAP between 65-70 mmHg.

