## 10. Goals

Primary goal: Change in norepinephrine requirement by at least 0.1 micrograms / kg / min to maintain similar MAP after initiation of CRRT with Oxiris membrane compared to standard AN69 membrane. MAP measurements will be performed hourly and norepinephrine requirement will be recorded at that time.

Exploratory goals:

- Effectiveness of the AN69-Oxiris membrane in reducing interleukin serum levels (IL 6, IL 10, and TNF alpha).

Serum will be taken every 8 hours for its measurement by ELISA method.

- To establish the safety (the same risk infection and bleeding) of using the AN69- Oxiris membrane in patients with AKI and COVID-19 infection who require CRRT.

Gross bleeding events (gastrointestinal or urinary) as well as catheter-associated infection events (criteria according to IDSA) will be recorded.

- Length of stay in UCI among patients who used AN69-Oxiris membrane in compared to the use of a conventional membrane (standard AN-69) in critically ill patients with COVID-19 associated AKI and CRRT requirement.

- To investigate the effect of AN69-Oxiris in reducing 28-day mortality in contrast compared with the effect of a conventional membrane in this population.

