#### 12. Outcomes

Outcomes:

-Primary outcome: to establish the superiority of treatment with the AN69-Oxiris membrane to sustain a similar MAP with a lower requirement of norepinephrine (at least 0.1 micrograms/kg/min) after 72 hours of treatment initiation, in patients with COVID-19 associated AKI requiring CRRT, compared to the usage of a standard AN69 membrane.

-Secondary outcomes:

- To evaluate the effectiveness of the AN69-Oxiris membrane in reducing interleukin serum levels (IL 6, IL 10, and TNF alpha).
- To demonstrate the advantage of the AN69-Oxiris membrane in decreasing 28-day mortality from the start of CRRT.
- To establish the safety of using the AN69-Oxiris membrane in patients with AKI and COVID-19 infection who require CRRT.
- To examine the efficacy of the AN69-Oxiris membrane in reducing the length of ICU stay compared to the use of a conventional membrane (standard AN-69) in critically ill patients with COVID-19 associated AKI and CRRT requirement.

Variables:

Acute kidney injury. Elevation in serum creatinine or decrease in the urinary output according to what is established in the KDIGO guidelines.

Mean arterial pressure. MAP is considered as the perfusion pressure for organs and, a value greater than 60 mmHg is adequate to maintain perfused the organs of an average person. The mean arterial pressure will be registered, either obtained through a peripheral arterial line (calculated from the area under the curve of the arterial pressure graph) or the non-invasive monitor using the oscillometric method.

Furosemide stress test: This term refers to a furosemide bolus of 1 mg/kg (ideal body weight) with subsequent measurement of urine output after 2 hours. It is considered negative when the urine output during this interval is less than 200 ml.

Safety variables:

\* Clotting of the circuit: it is defined as the presence of clots in the circuit lines and/or filter, which condition rise in the transmembrane, pre-filter, or post-filter pressures, warranting a change of the filter.

\* Allergic reaction: the sudden presence of erythema or rash at any time after starting CRRT treatment.

\* Access bleeding: the occurrence of continuous bleeding at the vascular access insertion site any time after the start of CRRT treatment.

\* Catheter-related bloodstream infection: the presence of any microorganism in blood cultures drawn from catheter's lumen.

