#### 16. Statistical analysis

Descriptive statistics will be used with measures of central tendency and dispersion of the data according to their distribution. The distribution of the variables will be analyzed with the Kolmogorov-Smirnov "Z" test. For categorical variables, frequencies and percentages will be used. For continuous variables with normal distribution, the mean and standard deviation will be shown. In contrast, the median and interquartile range will be used for continuous variables with an abnormal distribution.

The Student's t-test will be used to compare continuous variables between the two groups, in case of a normal distribution. The Mann-Whitney U-test will be performed for groups with an abnormal distribution. The analysis of data inside the same group at different time intervals (baseline vs 72 h) will be carried out using the Student's t-test, Wilcoxon sum of ranks, or McNemar's test, as appropriate.

Multivariate analysis for mortality will be performed using Cox proportional hazards, adjusted for the baseline SOFA score. Statistical analysis and graphs will be obtained using SPSS 19.0 software (Chicago, IL) and Graphpad Prism 5 software (San Diego, Ca), respectively. A p-value <0.05 will be considered significant. An intention-to-treat analysis will be pursued.

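### Cytokines are sampled every 8 hours for 72 hours, but Section 16 names no between-arm analysis that uses the series or adjusts for baseline

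*Combined protocol and SAP*

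**What the plan says.** Sampling is stated twice. Section 11 (Monitoring of interventions) says "Blood samples will be drawn, every 8 hours during the 72 hours of treatment, to measure cytokine serum levels", and Section 10 says "Serum will be taken every 8 hours for its measurement by ELISA method".

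Section 12 lists the matching secondary outcome: "To evaluate the effectiveness of the AN69-Oxiris membrane in reducing interleukin serum levels (IL 6, IL 10, and TNF alpha". It gives no time point and no summary measure. Section 10 calls the same aim exploratory.

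Section 16 gives these methods for continuous data:
- Between arms, Student's "t-test will be used to compare continuous variables between the two groups, in case of a normal distribution"; otherwise, "The Mann-Whitney U-test will be performed for groups with an abnormal distribution". No time point and no input variable (level, change, average) is named.
- Within an arm: "The analysis of data inside the same group at different time intervals (baseline vs 72 h", by paired-type tests.

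The only model is for another outcome: "Multivariate analysis for mortality will be performed using Cox proportional hazards, adjusted for the baseline SOFA score". The significance rule is "A p-value <0.05 will be considered significant", with no multiplicity rule. The section declares intention-to-treat but does not say what happens to samples missing after death or after CRRT stops.

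**The concern.** Cytokine removal is the mechanism on which the trial's rationale rests, and with 18 patients per arm precision is scarce. The sampling is intensive, yet no stated method is tied to the series.

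Each way of applying Section 16 to these data has a weakness:
- **Two-group test at 72 h.** Nine of the ten samples per cytokine are unused. Patients without a 72-h sample drop out, which sits badly with intention-to-treat in ventilated patients on vasopressors.
- **Within-arm baseline v 72 h.** Eight of ten samples are unused. A fall in one arm does not show that the membrane caused it, because the arms are not compared.
- **Two-group test at every sampling time.** Up to 27 post-start tests, each judged at 0.05.
- **Two-group test on a summary chosen later.** The choice is open until the data are seen, in an open-label trial.

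At stake is whether the trial gives one interpretable estimate of the membrane's effect on each cytokine.

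**Working it through.** **Plan's own figure.** There is none for cytokines. The only calculation is for norepinephrine (Section 13: difference 0.10, SD 0.10, two-sided 5%, 80% power). It reproduces: with the noncentral t distribution, 17 per arm gives 80.7% power and 16 gives 78.1%, so 34 in total.

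**Samples.** 72/8 = 9 post-start samples, or 10 with baseline. A 72-h test uses 1 of 10. A baseline v 72 h test uses 2 of 10.

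**Precision.** The documents give no cytokine correlations or SDs. I assume equal variance over time (set to 1, on the log scale) and complete data. The comparator is a raw two-group test at 72 h, with variance 1. The alternative is the mean of the nine post-start samples, adjusted for baseline:

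relative variance = variance of the nine-sample mean − (mean correlation of those samples with baseline)²

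Compound symmetry, (1 + 8ρ)/9 − ρ²:
- ρ = 0.3: 0.378 − 0.090 = 0.288
- ρ = 0.5: 0.556 − 0.250 = 0.306
- ρ = 0.7: 0.733 − 0.490 = 0.243

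AR(1), correlation per 8 h:
- 0.7: 0.445 − 0.249² = 0.383
- 0.8: 0.572 − 0.385² = 0.424
- 0.9: 0.750 − 0.613² = 0.375

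So the range is 24-42%, equivalent to 1/0.424 = 2.4 up to 1/0.243 = 4.1 times as many patients **if the treatment effect is constant from 8 to 72 h**. Against a baseline-adjusted 72-h comparison, whose variance is 1 − (correlation of baseline with 72 h)², the ratios are 0.32, 0.41 and 0.48 (compound symmetry) and 0.38, 0.43 and 0.44 (AR(1)).

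**Effect shape.** Suppose instead that the effect rises linearly to its full size at 72 h. The average then carries (1/9 + 2/9 + … + 9/9)/9 = 5/9 of the 72-h effect, and (5/9)² = 0.309. Information relative to the raw 72-h test is 0.309 divided by the relative variance:
- Compound symmetry: 0.309/0.288 = 1.07; 0.309/0.306 = 1.01; 0.309/0.243 = 1.27
- AR(1): 0.309/0.383 = 0.80 (0.805 unrounded); 0.309/0.424 = 0.73; 0.309/0.375 = 0.82

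**Multiplicity.** 9 times × 3 cytokines = 27 post-start tests. If independent, 1 − 0.95^27 = 0.75. They are not: a simulation of 27 null t-tests with 18 per arm, using the correlations above and three mutually independent cytokines, gave 0.69, 0.62 and 0.50 (compound symmetry) and 0.63, 0.56 and 0.44 (AR(1)). Correlation between cytokines would lower these further. Three single contrasts give 1 − 0.95³ = 0.14 if independent.

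**The case against.** The strongest reply is that Section 16 never specifies an unadjusted 72-h cytokine comparison between arms. Only the within-arm clause is tied to 72 h; the two-group sentence could be applied to a change, an area under the curve or a patient mean. This stands. A reader might infer that the stated method discards most of the data, keeps only 72-h survivors and is several times less precise than it could be. The documents do not support that as a statement about the plan: it describes one possible application of an open sentence. The other applications still leave the measure unspecified or invite many tests.

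Second, the precision gain depends on effect shape, which the documents do not give. This also stands, as the linear case shows. An 8-72 h average is also a different quantity from the 72-h level, and the research question in Section 9, although it concerns vasopressor dose, is framed at 72 hours.

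Third, a mixed model is not assumption-free. An unstructured 9 × 9 covariance has 9 × 10/2 = 45 parameters for 36 patients. A likelihood analysis also treats samples missing after death as missing at random. Both points stand and are met in the fix. The exclusions for short life expectancy and SOFA above 11 (Section 15) may limit early loss, but do not remove it.

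Fourth, cytokines are not the primary outcome. That limits the priority. It is no reason to leave the analysis open when the samples are already planned.

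**Conclusion.** The point holds as a gap in the analysis plan with a concrete, better alternative. No method in Section 16 uses the 8-hourly series or adjusts for baseline, and the one explicit longitudinal comparison is within arms, so it does not test the treatment effect.

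The size is conditional. With a roughly constant effect, the averaged contrast has about 24-42% of the variance of a raw 72-h comparison (assumed compound symmetry 0.3-0.7 or AR(1) 0.7-0.9 per 8 h). With an effect that builds linearly, relative information is 0.73-1.27. A multiple of 2.4 to 4.1 in patient numbers should therefore not be read as an established loss.

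The 75% false-positive chance is an upper illustration. A reader might count 30 tests and reach 1 − 0.95^30 = 79%, but that includes baseline, which is not a treatment comparison, and ignores correlation.

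The gains that do not depend on effect shape are a single prespecified randomised contrast per cytokine and the use of samples from patients who lack a 72-h value. The primary outcome and sample size are unaffected. This is a low-cost improvement.

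**What to change.** In Section 16, add a cytokine paragraph:
- Analyse each log-transformed cytokine with a mixed model for repeated measures: baseline value, arm, time, arm-by-time and site. Prespecify a parsimonious covariance structure and a small-sample degrees-of-freedom method.
- Name one primary between-arm contrast per cytokine: the 8-72 h average, with the 72-h contrast from the same model as supportive. If the investigators regard the 72-h level as the quantity of interest, they should say so now and reverse the two. Report geometric mean ratios with 95% CIs.
- State how samples missing after death are interpreted, and that the model assumes other missing samples are missing at random.
- Keep within-arm changes as description only.
- Confirm that a sample before CRRT starts is part of the schedule, since Section 11 does not say so and Section 16 only implies it.

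Section 20 defers the assays until recruitment ends, so this can be fixed before any cytokine result exists. The cost is a little more analysis and no new patients, samples or assays. The price is reliance on missing-at-random and, with the average as primary, a quantity that differs from the 72-h level.

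### Does the dialysate formula break down in the upper part of the citrate dose range?

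*Combined protocol and SAP*

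**What the plan says.** Section 11, Monitoring of interventions, sets one prescription for both groups: "All renal replacement therapy prescriptions (control and intervention group) will be standardized as follows". The parts that matter here are:

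- Effluent: "The dose of CRRT will be set at 30ml/kg/h, using ideal body weight".
- Modality: "CRRT modality: Continuous veno-venous hemodiafiltration".
- Citrate solution: "Gambro Prismocitrate 18/2-citrate 18 mmol/L".
- Basis of the citrate dose: "Initial citrate dose will be determined according to the processed blood volume".
- Flow and range that go with that dose: "maintaining a blood flow of 150mL/min, in close relation to a citrate dose of 2.5-5mmolL".
- Post-dilution fluid at 150 mL/h, and ultrafiltration at 100 mL/h for the first 4 hours, then adjusted on clinical grounds.
- Dialysate: "The dialysate flow rate will be determined as the remaining fluid obtained using the following formula", namely total effluent minus the sum of citrate, post-dilution fluid and ultrafiltration.

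The section also says how the citrate dose is chosen: "Calculations to determine initial citrate dose will be performed using Adequator mobile application". Later citrate monitoring and dosing follow institutional protocols in supplemental material 1, which is not part of the supplied text. The circuit ionized calcium target is 0.2 to 0.4 mmol/L. Delivered effluent dose is to be checked from BUN before and after the filter.

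**The concern.** Every term in the dialysate formula except body weight is printed, so it can be tested from the document. The citrate solution is dilute, so a dose that scales with blood flow takes up a large volume. That volume is subtracted from an effluent total that scales only with ideal weight. In a lighter patient, or at a higher citrate dose, the subtraction can give zero or less.

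A negative dialysate rate cannot be delivered. If dialysate were simply set to zero, effluent would exceed the stated 30 mL/kg/h, and the treatment would have no dialysate component although hemodiafiltration is specified. The dose described as standardized would then vary with weight and citrate dose. In a trial of 36 patients, uncontrolled variation in co-treatment could add noise to norepinephrine dose at 72 hours, the main outcome. The supplied text gives no rule for a remainder that is not positive.

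**Working it through.** The protocol states no dialysate rate, so there is no figure to reproduce. The check asks whether the printed values fit together.

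**Inputs from section 11.** Effluent is 30 mL/kg/h. Blood flow is 150 mL/min = 150 × 60 / 1,000 = 9 L/h. Citrate solution is 18 mmol/L. Citrate dose c runs from 2.5 to 5. Post-dilution is 150 mL/h and initial ultrafiltration 100 mL/h, together 250 mL/h.

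**Assumptions.** Ideal weight W of 60, 70 and 80 kg; for the plasma reading, haematocrit h of 30%, with a range of 25% to 40%. The document gives neither.

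**Reading 1: mmol per litre of blood.**
- Citrate flow = 9c / 18 × 1,000 = 500c mL/h, so 1,250 to 2,500 mL/h over the range.
- Dialysate = 30W − 500c − 250.
- Zero at c = (30W − 250) / 500: 1,550/500 = 3.1 at 60 kg, 1,850/500 = 3.7 at 70 kg, 2,150/500 = 4.3 at 80 kg.
- At 70 kg: 2,100 − 1,250 − 250 = +600 mL/h at c = 2.5, and 2,100 − 2,500 − 250 = −650 mL/h at c = 5.
- The lowest dose leaves a positive remainder above (1,250 + 250)/30 = 50 kg. The whole range does so only above (2,500 + 250)/30 = 91.7 kg.
- With c = 5 and dialysate set to zero, effluent is 2,750/W: 45.8, 39.3 and 34.4 mL/kg/h at 60, 70 and 80 kg.

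**Reading 2: concentration in the blood–citrate mixture.**
- Citrate flow = 9,000c / (18 − c).
- With R = 30W − 250, zero is at c = 18R / (9,000 + R): 2.64, 3.07 and 3.47 at 60, 70 and 80 kg. The conflict is wider than in reading 1.

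**Reading 3: mmol per litre of plasma.**
- Citrate flow = 500c(1 − h).
- Zero at c = (30W − 250) / (500(1 − h)). At h = 30%: 1,550/350 = 4.43, 1,850/350 = 5.29 and 2,150/350 = 6.14.
- The last two lie above the range. The whole range works above (1,750 + 250)/30 = 66.7 kg.
- At 70 kg the zero point runs from 4.93 (h = 25%) to 6.17 (h = 40%).

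**Reading 4: mmol per hour.**
- Citrate flow = 2.5/18 × 1,000 = 139 to 5/18 × 1,000 = 278 mL/h.
- At 70 kg and the top dose, dialysate = 2,100 − 278 − 250 = 1,572 mL/h. There is no conflict.

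The same printed numbers therefore give anything from a wide conflict to none, depending on a denominator the text does not state. The zero points also describe only the first 4 hours: with ultrafiltration at 0, reading 1 at 70 kg gives (2,100 − 150)/500 = 3.9, and a higher rate moves the point down.

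**The case for a change.** The best case for acting is that reading 1 is the natural one. The sentence ties the dose to the volume of blood processed and to a stated blood flow, and the printed unit contains both mmol and L. On that reading, much of the range cannot be combined with the other fixed values at common weights, and at 50 kg or below none of it can. The protocol promises a standardized prescription and a check of delivered dose against it; a target that its own formula cannot always reach weakens both. Stating the unit would cost little.

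The arithmetic and the preference for reading 1 stand. The step from there to a needed change is weaker, for four reasons.

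- The unit is garbled, and a slash may have been lost when the PDF was read.
- A range is not an instruction to use every dose at every weight. The starting dose is calculated for the individual patient and steered by the circuit calcium target.
- The natural place for a rule on a non-positive remainder is the supplement. As it was not supplied, the rule cannot be called missing.
- The pre- and post-filter BUN check already examines delivered dose. It does not repair a negative remainder, but it bears on how far actual treatment departs from the prescription.

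The trial is open-label, so handling could in principle differ by arm. However, one formula and one calcium target apply to both, and nothing in the document points to a difference.

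**Conclusion.** No change to the plan follows. If the dose is per litre of processed blood, the formula leaves no dialysate from 3.1, 3.7 and 4.3 mmol/L upward at assumed ideal weights of 60, 70 and 80 kg, and across the whole range at 50 kg or below. That result rests on an unclear unit, assumed weights and the initial ultrafiltration rate. It largely disappears per litre of plasma and is absent per hour.

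What remains is a missing detail. A clinician whose calculation gives a negative rate will see it at the bedside and adjust; which element then gives way is a clinical matter on which this review takes no position. The prescription is common to both arms, and the calculation in section 13 uses only the norepinephrine difference and its standard deviation. The number of patients affected cannot be estimated, because the document gives neither weights nor citrate doses used. Spelling out the unit would be an editorial courtesy, with no demonstrated gain for the comparison.
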